## Toxicity monitoring

Toxicity will be monitored closely for each treatment arm using the method of Thall et al (1995). Denote the probability of toxicity by  $P_E$ , where toxicity is defined as any treatment-related grade 3 or greater non-hematological toxicities. We assume  $P_E \sim \text{beta}(0.6, 1.4)$ . We will stop the trial if at any point  $\Pr(P_E > 0.30 \mid \text{data}) > 0.95$ . That is, we will stop the trial if, at any time during the study, we determine that there is more than 95% chance that the toxicity rate is more than 30%. The trial will be stopped if (the number of toxicity observed / among number of patients)  $\geq 6/10, 11/20, 15/30, 19/40, 22/50, 26/60, 30/70, 34/80, 38/90, 42/100, 46/110, 49/120, 53/130$ . The operating characteristics are listed in table 2.

Table 2: The operating characteristics for toxicity monitoring are summarized in the following table

True toxicity probability	Probability of early stop	Sample size percentiles (10, 25, 50, 75, 90)
0.1	0.0002	140 140 140 140 140
0.2	0.008	140 140 140 140 140
0.3	0.095	140 140 140 140 140
0.4	0.666	10 30 70 140 140
0.5	0.995	10 10 20 40 60

AdaptiveRandomization 4.1.1 software and Multic99 were used for the trial design.

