### **Phase II**

The phase II portion of the study will include only newly diagnostic AML patients, and the primary objective is to compare the event-free survival (EFS) between treatment CIA and FLAI, where event is defined as be resistance to treatment, relapse (after response) or death, whichever occurred first.

A maximum of 200 front-line patients will be enrolled in the study. To enroll 200 front line patients, the total sample size (front-line and salvage patients combined) is 280.

This section will focus on front-line patients only. An adaptive randomization algorithm will be used to assign the patients to the two treatment arms. Initially 40 patients will be randomized equally to the two treatment arms. After the completion of the equal randomization, the adaptive randomization algorithm will be employed to unbalance the

randomization probabilities in favor of the treatment arm with a better event free survival. The expected accrual rate is about 5 patients per month, and the additional follow-up time is 12 months after all patients have been enrolled to the study.

The historical data suggested the median event free survival time for FLAI treatment was 5 months. Let  $\theta_1$  and  $\theta_2$  denote the median event free survival time for treatment arm CIA and FLAI respectively, we assume the prior for the median event free survival time follows Inverse Gamma (IG) distribution:  $\theta_1 \sim \text{IG}(3, 10)$ , and  $\theta_2 \sim \text{IG}(3, 10)$ . Each time a new patient enters the trial, be the posterior probabilities  $\pi_i = \Pr(\theta_i > \theta_j \mid \text{data})$  will be calculated ( $i, j = 1, 2$ ). The randomization probability to treatment arm CIA and FLAI will be the posterior probabilities  $\pi_i = \frac{\sqrt{\pi_i}}{\sqrt{\pi_1} + \sqrt{\pi_2}}$ .

The trial will be stopped early for both efficacy and futility based on the follow stopping rules. Table 1 presents the operating characteristics of simulations based on the described design.

1. Early loser selection: Suspend accrual to an arm  $i$  if  $\Pr(\theta_i < \theta_{j \neq i} \mid \text{Data}) < 0.025$
2. Early winner selection: Stop the trial and select an arm  $i$  as superior if  $\Pr(\theta_i > \theta_{j \neq i} \mid \text{Data}) > 0.975$
- 3 Final winner selection: At the final analysis after all patients have been evaluated, select arm  $i$  as superior if  $\Pr(\theta_i > \theta_{j \neq i} \mid \text{Data}) > 0.975$

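### The worded toxicity rule, the listed stopping boundaries and Table 2 describe three different procedures, so Table 2's stop probabilities do not belong to the rule as written.

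*Combined protocol and SAP*

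**What the plan says.** Section X, Toxicity monitoring, contains four elements.

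- **Unit and action.** "Toxicity will be monitored closely for each treatment arm". The consequence is stated for the trial: "We will stop the trial if at any point" the posterior criterion is met. The rule is then repeated in words, with the same trial-level action: "we will stop the trial if, at any time during the study, we determine that there is more than 95% chance" (of toxicity above 30%). The sentence that introduces the boundaries also speaks of stopping the trial.
- **Criterion.** Prior beta(0.6, 1.4) for the toxicity probability; stop when Pr(P_E > 0.30 | data) > 0.95.
- **Boundaries.** Toxicities over patients: "6/10, 11/20, 15/30, 19/40, 22/50, 26/60, 30/70, 34/80, 38/90, 42/100, 46/110, 49/120, 53/130". They exist only at multiples of 10.
- **Table 2.** One set of early-stop probabilities (0.0002, 0.008, 0.095, 0.666, 0.995 at true rates 0.1 to 0.5). The sample-size percentiles end at 140; the first three rows read "140 140 140 140 140".

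No trial-level stop probability is given. Nothing says that a crossing closes only the affected arm, or that looks occur only every 10 patients. The Phase II part of the same section does separate the two actions for event-free survival (EFS): its first rule suspends one arm, its second ends the trial.

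**The concern.** Monitoring each arm while stopping the trial gives two chances to stop, and checking at any time gives more chances than checking every 10 patients. A single-arm table with looks every 10 would then understate how often the trial stops when toxicity is acceptable. The boundary list should also follow from the stated prior and cutoff, and it does not.

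This is the phase II safety stopping rule. As written, two people could take opposite decisions on the same data: at 10 toxicities in 20 patients the posterior sentence says stop, and the list says continue. A crossing in one arm, read literally, also ends accrual to the other arm and with it the comparison of CIA with FLAI.

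**Working it through.** **Inputs.** From Toxicity monitoring: the prior, the 0.30 threshold, the 0.95 cutoff, the 13 boundaries and the maximum of 140. From Phase II: "A maximum of 200 front-line patients will be enrolled in the study", and 280 in total with salvage patients (280 / 2 = 140). From Table 1: mean arm sizes 88.2 and 87.1 in Scenario 1, and 74.8 and 50.6 in Scenario 3.

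**Method.** Exact binomial recursion. With f_n(x) the probability of x toxicities in n patients without an earlier stop, f_n(x) = (1 − p)·f_{n−1}(x) + p·f_{n−1}(x − 1). At each look, the mass at or above the boundary is removed and added to the stop probability. A crossing on an arm's last patient is not counted as early. For two independent arms, the chance that either stops is 1 − (1 − p1)(1 − p2).

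**Step 1: reproduce Table 2.** One arm, maximum 140, listed boundaries at 10, 20, ..., 130:

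| True rate | Table 2 | Recomputed |
|---|---|---|
| 0.1 | 0.0002 | 0.00015 |
| 0.2 | 0.008 | 0.0068 |
| 0.3 | 0.095 | 0.0893 |
| 0.4 | 0.666 | 0.657 |
| 0.5 | 0.995 | 0.994 |

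All differences are below 0.01 and every sample-size percentile matches. Table 2 is therefore a one-arm table with looks every 10.

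**Step 2: either arm stops the trial, listed boundaries every 10, both arms at 30%.**
- 140 per arm: 1 − (1 − 0.0893)² = 0.171. With Table 2's own figure, 1 − 0.905² = 0.181.
- 100 per arm: 0.165.
- 88/87: 0.163.
- 75/51: 0.154.
- 50 per arm: 0.129.

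The stated 0.095 is 0.095 / 0.171 = 56% to 0.095 / 0.129 = 74% of these. At 40% in both arms the figures are 0.88 (140 per arm), 0.79 (88/87) and 0.55 (50 per arm), against 0.666 stated.

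**Step 3: do the boundaries follow from the stated rule?** After x toxicities in n patients the posterior is beta(0.6 + x, 1.4 + n − x). At 10/20 this is beta(10.6, 11.4), with Pr(P_E > 0.30) = 0.961, which already exceeds 0.95; the list has 11/20 (0.986). At 130 patients the cutoff is met at 48, and the listed 53 has posterior 0.995. The full set from the worded rule is 6/10, 10/20, 14/30, 18/40, 21/50, 25/60, 28/70, 32/80, 35/90, 38/100, 42/110, 45/120, 48/130. Only 6/10 agrees with the list; the other 12 listed values are higher.

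Effect at 30%, looks every 10, 140 per arm: one arm 0.170 instead of 0.089; either arm 1 − (1 − 0.170)² = 0.311.

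**Step 4: worded cutoff after every patient, either arm.**
- At 30%, 140 per arm: one arm 0.251, so 1 − (1 − 0.251)² = 0.439. With 100 per arm it is 0.405, with 88/87 it is 0.391, and with 50 per arm it is 0.34.
- If looks start at patient 10, the range for 50 to 140 per arm is 0.29 to 0.40.
- At 20%: 0.05, or 0.026 if looks start at patient 10, against 0.008 stated.

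**The case against.** The best defence is that the intention was per-arm closure with looks every 10 patients. The monitoring sentence names each arm, the cited method is for single-arm trials, the boundary list can be read as the operative schedule, and 140 is half of 280. On that reading the two-arm inflation disappears. This is plausible, but the text does not say it, and the Phase II part shows that the authors distinguish suspending an arm from stopping the trial. Nor does it remove the boundary mismatch: while the 0.95 sentence stands, one arm checked every 10 stops with probability 0.170 at a true rate of 30%, not 0.095.

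Three stronger readings are tempting and should be resisted.

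- **That Table 2 is miscalculated.** It is not; it reproduces from the listed boundaries.
- **That the stated false-stop rate is half the true one or less.** With the listed boundaries and looks every 10, 0.095 is 56% to 74% of the trial-level figure for 50 to 140 per arm. Assuming 140 in both arms is generous, given the front-line cap of 200, adaptive allocation and early EFS stopping.
- **That the 0.44 comes from the second arm and continuous looks alone.** Part of it is the boundary mismatch in Step 3. The 0.44 and the 0.05 at 20% also rely on looks before patient 10, since the worded cutoff is met at 3 toxicities in 3 patients.

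If one arm has 40% toxicity and the other 10%, literal wording closes the less toxic arm with probability about 0.66. That restates Table 2's 0.666 as a consequence of the wording and is not a separate error.

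**Conclusion.** The concern holds as an internal inconsistency between the worded rule, the boundary list and Table 2. Three differences contribute at 30% toxicity in both arms, against 0.095 stated:

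- either-arm stopping with the list as given: 0.13 to 0.17;
- boundaries that do not follow from the stated prior and cutoff: 0.17 in one arm of 140, 0.31 for either arm, looks every 10;
- checking the worded cutoff after every patient, either arm: 0.34 to 0.44, or 0.29 to 0.40 from patient 10.

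The either-arm ranges cover 50 to 140 per arm and assume independent arms of fixed size. Adaptive allocation and EFS stopping would change them. The small differences from Table 2 are consistent with simulation error, but the number of simulations is not stated.

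All 13 listed values are reproduced if the fixed 0.30 is replaced by a beta(30, 70) comparator. That is an inference about how the list arose; the documents do not mention it. They do not show which of the three descriptions was intended, and this review does not choose among them.

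**What to change.** Reconcile the passages so that one rule is described throughout:

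1. State whether a crossing closes the affected arm or the trial.
2. State the look schedule, including the first look.
3. Make the boundary list and the posterior criterion agree. If the comparator is not a fixed 0.30, state its distribution.
4. Recalculate Table 2 for the resulting rule, per arm and for the trial, with arm sizes realistic under adaptive allocation and EFS stopping.

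Settling points 1 and 2 alone, as arm closure every 10 patients, would not make Table 2 correct while the present cutoff sentence stays.

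The cost is a few sentences and one recalculated table. A stated figure may become less favourable.

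### Table 2's toxicity stopping probabilities assume an arm can run to 140 patients, a size phase II as described rarely reaches; under the listed boundaries they are too favourable at the expected arm sizes

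*Combined protocol and SAP*

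**What the plan says.** Under Toxicity monitoring, the unit is the arm: "Toxicity will be monitored closely for each treatment arm". The toxicity probability has a beta(0.6, 1.4) prior, and the trial stops once "there is more than 95% chance that the toxicity rate is more than 30" per cent. The section then lists boundaries every 10 patients: "6/10, 11/20, 15/30, 19/40, 22/50, 26/60, 30/70, 34/80, 38/90, 42/100, 46/110, 49/120, 53/130". Table 2 reports early-stop probabilities of 0.0002, 0.008, 0.095, 0.666 and 0.995 at true toxicity 0.1 to 0.5. Its sample-size percentiles are "140 140 140 140 140" at the lower toxicity rates and "10 30 70 140 140" at 0.4, so 140 is the size at which an unstopped run ends.

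The Phase II section states: "A maximum of 200 front-line patients will be enrolled in the study". It adds that "the total sample size (front-line and salvage patients combined) is 280", but also that "The phase II portion of the study will include only newly diagnostic AML patients". After 40 equally randomized patients, allocation moves toward the arm with better EFS, and a posterior probability above 0.975 stops the trial early.

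Table 1 gives the resulting mean arm sizes (Arm 1 / Arm 2): 88.2 / 87.1, 22.5 / 27.7, 74.8 / 50.6, 62.3 / 40 and 43.7 / 30.5 in Scenarios 1 to 5. The 97.5% limits run from 35 to 140.

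**The concern.** Tables 1 and 2 appear to describe trials of different size. Table 2 carries each arm to 140 patients. Half of 200 is 100, and Table 1's largest mean is 88.2. Because the chance of crossing a boundary accumulates over looks, an arm that ends sooner has fewer chances to stop. Table 2 is the only quantitative description of how the toxicity rule performs. A monitoring or ethics committee reading it would take the chance of stopping an arm with 40% toxicity to be two in three, and might accept the rule on that basis.

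**Working it through.** **Inputs.** Listed boundaries at n = 10 to 130 and the 140 maximum: Toxicity monitoring and Table 2. Cap of 200, total of 280, prior and stopping rules for EFS: Phase II section. Mean arm sizes: Table 1.

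**Method.** With p the true toxicity rate, the distribution of the toxicity count X is carried forward one patient at a time: P(X = x at n) = (1 − p)·P(X = x at n − 1) + p·P(X = x − 1 at n − 1). At each look, all probability at or above the listed boundary is removed and added to the stopping probability.

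**Step 1: reproduce Table 2 (maximum 140, last look at 130).**

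| True toxicity | Recomputed | Stated |
|---|---|---|
| 0.1 | 0.0001 | 0.0002 |
| 0.2 | 0.0068 | 0.008 |
| 0.3 | 0.089 | 0.095 |
| 0.4 | 0.657 | 0.666 |
| 0.5 | 0.994 | 0.995 |

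The percentiles match too. At 0.4 the cumulative stopping probability is 0.166 at 10 patients, 0.216 at 20, 0.278 at 30, 0.474 at 60 and 0.511 at 70, and it ends at 0.657. The 10th, 25th and 50th percentiles are therefore 10, 30 and 70, and the 75th and 90th are 140, as printed.

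**Step 2: the same boundaries with a smaller arm.** An arm of 88 has its last look at 80, one of 75 at 70 and one of 51 at 50.

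| Arm size | Stop at 0.4 | Stop at 0.5 |
|---|---|---|
| 140 | 0.657 | 0.994 |
| 100 (200/2), look at 100 counted | 0.585 | 0.979 |
| 100, last look at 90 | 0.56 | 0.97 |
| 88 | 0.540 | 0.959 |
| 75 | 0.511 | 0.942 |
| 51 | 0.426 | 0.874 |
| 30 | 0.278 | 0.658 |
| 22 | 0.216 | 0.512 |

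Measured from the recomputed 0.657, the gap at 40% toxicity is 0.657 − 0.585 = 0.072 at 100, 0.117 at 88 and 0.231 at 51. At 50% toxicity it is 0.994 − 0.979 = 0.015 at 100.

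**Step 3: allow for the spread of arm sizes.** A mean is not a fixed size, so the adaptive design was simulated with 4,000 trials per scenario. The settings were exponential EFS, the IG(3, 10) prior on the median, square-root weights, the 0.975 rule after 40 patients, 5 patients a month and a maximum of 200. The simulation gives Table 1's means within about 3 patients and its selection probabilities within about 2.5 points. Averaging the step 2 curve over the simulated arm sizes, with toxicity taken as independent of EFS:

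| Scenario | Arm 1, at 0.4 / 0.5 | Arm 2, at 0.4 / 0.5 |
|---|---|---|
| 1 | 0.51 / 0.90 | 0.51 / 0.90 |
| 2 | 0.22 / 0.52 | 0.25 / 0.57 |
| 3 | 0.47 / 0.85 | 0.37 / 0.75 |
| 4 | 0.41 / 0.79 | 0.31 / 0.68 |
| 5 | 0.33 / 0.70 | 0.26 / 0.59 |

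An arm reached 140 in at most about 2% of simulated trials.

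**Step 4: the worded rule.** After x toxicities in n patients the posterior is beta(0.6 + x, 1.4 + n − x). At 10 of 20 it is beta(10.6, 11.4), which puts probability 0.961 above 0.30. The worded rule therefore already stops at 10/20, where the list says 11/20. At the same looks it gives 6/10, 10/20, 14/30, 18/40, 21/50, and so on to 38/100 and 48/130. Its stopping probability at 40% toxicity is 0.54 at 51 patients, 0.65 at 75, 0.69 at 88, 0.78 at 100 and 0.86 at 140.

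**The case against.** **140 has a visible source.** The total of 280 halves to 140, and the toxicity section does not say it is confined to front-line patients. This is probably where the figure came from, and Table 2 is arithmetically right for that maximum. But it describes the trial only if salvage patients are counted in the rule, allocation is equal and no EFS stop occurs. The Phase II section and the inclusion criteria limit entry to newly diagnosed AML, allocation is adaptive, and the EFS rules are part of the design. Scaling every simulated arm by 280/200 = 1.4 (an assumption) gives about 0.24 to 0.57 at 40% toxicity and 0.57 to 0.93 at 50%, still below Table 2.

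**An arm can exceed 100.** This stands. Four of Table 1's ten arm rows have 97.5% limits of 134 to 140. A reader might infer that the cap of 200 holds each arm to 100; it does not. These limits are upper tails, however, not expected sizes.

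**No patient loses protection.** This stands in large part. The boundaries do not depend on the maximum, so through any given number of patients the chance of having stopped is the same. Where an arm is small because EFS closed it, fewer patients were exposed. A reader might infer that the rule leaves patients unprotected, and the documents do not support that. The point concerns what Table 2 tells its reader.

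**The rule stops the trial, so either arm can trigger it.** If both arms had 40% toxicity, independently, the chance at 88 per arm would be 1 − (1 − 0.54)² = 0.79. On the same footing the figure at 140 is 1 − (1 − 0.657)² = 0.88, so the gap remains, and Table 2 is reproduced as a single-arm table.

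**The worded rule is stricter.** This also stands. At 40% toxicity it gives 0.69 at 88 and 0.78 at 100, both above the stated 0.666. A reader might conclude that Table 2 overstates protection under any reading of the rule, and that would be wrong. The shortfall is established for the listed boundaries, which are the ones that reproduce Table 2.

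**Conclusion.** The point holds in limited form. Table 2 is correctly computed for an arm that can run to 140 patients, but that is not the phase II design the plan describes. Under the listed boundaries, the stopping probability at 40% toxicity is about 7 points lower at 100 per arm, 12 points lower at 88 and 23 points lower at 51. At 50% toxicity the loss is small at 100 per arm (1.5 points) and clear only in smaller arms. The results at fixed arm sizes are exact; those averaged over arm sizes rest on the simulation assumptions given above and on toxicity being independent of EFS. Part of the decline is early EFS closure with less exposure, so it should not be read wholly as lost safety. It should still be corrected, because readers rely on these figures and the correction is cheap.

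**What to change.** 1. State which patients count in the toxicity rule. If salvage patients do, say so and reconcile this with the eligibility criteria and with the statement of the phase II population.
2. Reconcile the listed boundaries with the worded posterior rule. The two cannot both be the rule in force, and Table 2 must be computed from whichever is kept.
3. Rerun Table 2 at 100 per arm, and over the arm-size distribution from the Table 1 simulation with the EFS stopping rules applied. State the assumed maximum and whether a look at the last patient is counted. Reporting patients exposed beside each stopping probability would separate early EFS closure from failure to detect toxicity.

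The cost is a rerun and a few sentences, with no extra patients. If the listed boundaries are kept, the stated figures become somewhat less favourable.

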### **Analysis method**

Data analysis will be performed using SAS or S-plus, as appropriate. The median EFS time will be estimated by Bayesian posterior estimates, along with the 95% credible intervals for both treatment arms. The posterior probability that one arm has a better EFS than the other arm will be also calculated.

Demographic and baseline laboratory results will be summarized using descriptive statistics, including means with standard deviations, or medians with ranges, histograms and box-plot. Fisher's exact test and Wilcoxon rank test will be used in the data analyses of categorical and continuous variables, respectively. Survival or times to failure and time to progression functions will be estimated using the Kaplan-Meier method. The two-sided log-rank test will be used to assess the differences of time to events between groups, and Cox proportional hazards model will also be fitted to compare the time-to-event outcomes between the two treatment arms adjusting for the effects of covariates. Toxicity will be reported by type, frequency and severity. Highest toxicity grades per patient per course will be tabulated for selected adverse events and laboratory measurements.

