**II. RATIONALE**

Treatment options for relapsed and refractory AML and high-risk MDS are limited.

Retreatment with a high-dose cytarabine (HDAC) containing regimen is considered standard for patients relapsing after an initial complete remission (CR) lasting for a year or more. Once a second remission is achieved, these patients can proceed to stem cell transplant if appropriate donors are available. For patients relapsing after a shorter

remission or with primary refractory disease no true standard options exist and investigational therapy is considered appropriate.

We have been using fludarabine and ara-C (FA) combination chemotherapy since 1989 for relapsed AML, and since 1991 for newly diagnosed AML/MDS. We have reported that FA is superior to ara-C in relapsed AML, if disease is sensitive to ara-C as manifested by a relatively long first remission. In patients with newly diagnosed disease, the use of FA- containing regimens was associated with higher complete response rates (50-60%) than with standard chemotherapy. The effectiveness of FA is believed due to the ability of fludarabine to modulate the pharmacologic behavior of ara-C. Specifically, at intracellular concentrations of  $\geq 10 \mu\text{M}$ , F-ara-ATP, the active metabolite of fludarabine, increases accumulation of ara-CTP in AML cells beyond that possible with dose escalation of ara-C. Once above  $10 \mu\text{M}$  F-ara-ATP, ara-CTP formation plateaus.

Single agent clofarabine has demonstrated activity in phase I studies in AML. As a potent inhibitor of ribonucleotide reductase (RNR) and by means of biochemical modulation, clofarabine is more ideally suited to be incorporated into combinations such as have been tested and validated with fludarabine and cytarabine in AML in the past. We have previously conducted a study combining cytarabine with clofarabine in patients with relapsed/refractory AML. At doses of  $1 \text{ g/m}^2$  daily x 5 for cytarabine and  $40 \text{ mg/m}^2$  daily x 5 for clofarabine, we reported a response rate of 40% (28% complete remission) in 29 patients with a median age of 59 years (18 to 84 years). Responses extended to

patients with primary refractory disease and those with abnormal cytogenetics. Other groups have since followed this lead and published comparable results, albeit doses of cytarabine and clofarabine varied throughout the different studies.

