Anthracyclines have been traditionally combined with cytarabine in AML. Two recent publications highlighted higher response rates and better disease-free survival in both younger and older patients with frontline AML when high-dose daunorubicin (90 mg/m^2/dose) was used in a “3+7” induction combination highlighting the activity of this class of agents for AML therapy. Pautas et al randomized 468 patients ages 50 to 70 years on Acute Leukemia French Association studies to 3 induction anthracycline regimens: idarubicin 12 mg/m^2 daily for 3 days, idarubicin 12 mg/m^2 daily for 4 days, and high-dose daunorubicin 80 mg/m^2 daily for 3 days. The CR rate with idarubicin daily for 3 days was higher than with high-dose daunorubicin (83% vs 70%), as was the 3-year event-free survival rate (23% vs 16%).

The combination with nucleoside analogs synergizes the anthracyclines activity by inhibiting DNA repair damage. Holowiecki et al from Poland randomized 673 patients (ages 18 to 60 years) to receive either daunorubicin plus cytarabine (DA), or DA plus fludarabine, or DA plus chlorodeoxyadenosine (DAC). The authors reported significantly higher CR rates after 1 course of induction and overall and reported better 3-year survival rates with the addition of the DAC regimen.

We have previously explored the combination of clofarabine, idarubicin, and cytarabine in a phase I study for patients with relapsed/refractory AML. The following doses were established for further evaluation: clofarabine 22.5 mg/m^2 daily x 5, idarubicin 6 mg/m^2 daily x 3, and cytarabine 0.75 mg/m^2 daily x 5. In a recent update of a phase II study of 63 patients treated with CIA, the overall response rate was 38% including 21% with complete remission. Median overall survival was 34 weeks for all patients and 66 weeks for those patients who achieved CR/CRp. Twenty-four patients (38%) were able to proceed with a stem cell transplant. Induction mortality was at 8%. Toxicities were manageable.

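### The EFS median is to be reported from a posterior that is in effect exponential; with failures clustered at the end of induction it would overstate the true median by an uncertain amount

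*Combined protocol and SAP*

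**What the plan says.** Section X, Phase II, makes EFS the basis of the comparison, "where event is defined as be resistance to treatment, relapse (after response) or death, whichever occurred first". It gives a control figure, "The historical data suggested the median event free survival time for FLAI treatment was 5 months", and a prior, "we assume the prior for the median event free survival time follows Inverse Gamma (IG) distribution", with IG(3, 10) for each arm (prior mean 10/(3-1) = 5 months). The posterior probability that one median exceeds the other drives the adaptive randomization, the early winner rule and the final winner rule. No survival distribution is named, and no check of one is planned.

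Under Analysis method, the EFS median is assigned to this posterior: "The median EFS time will be estimated by Bayesian posterior estimates, along with the 95% credible intervals for both treatment arms". Then: "The posterior probability that one arm has a better EFS than the other arm will be also calculated". The same section also plans Kaplan-Meier curves for times to failure, a two-sided log-rank test and a Cox model. It does not say which result prevails.

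Two other places bear on the shape of the EFS curve. The Rationale says that fludarabine/ara-C regimens in newly diagnosed patients gave a rate that "was associated with higher complete response rates (50-60%) than with standard chemotherapy". It also cites a randomized anthracycline trial at ages 50 to 70 with CR of 83% against 70% and 3-year EFS of 23% against 16%. Section VI lists only death and relapse as EFS events, without resistance.

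**The concern.** Under an exponential model the posterior median is, apart from the prior, ln 2 times total follow-up divided by the number of events. That equals the median only if the hazard is constant. If many patients fail at the response assessment and the rest stay event-free much longer, the long follow-up of the remitters raises this quantity while the true median stays low. At stake are the reported EFS median and its credible interval in each arm, and whether Table 1 describes the design for the median differences it lists. The trial could also publish a posterior median and a Kaplan-Meier median that disagree, with no rule for choosing between them.

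**Working it through.** **1. Is the model exponential?** With exponential EFS and IG(3, 10) on the median, the posterior is IG(3 + d, 10 + ln 2 × T), where d is events and T is person-months. Its mean is (10 + ln 2 × T)/(2 + d). I simulated the design with 40 patients randomized equally, then square-root weights, the 0.975 winner rule at each new patient, 5 patients per month, at most 200 patients and 12 further months.

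| True medians | Pr(select Arm 1), Table 1 | Simulated | Mean total N, Table 1 | Simulated |
|---|---|---|---|---|
| 5 v 5 | 0.12 | 0.136 | 175 | 170 |
| 2 v 5 | 0 | 0 | 50 | 50 |
| 7 v 5 | 0.757 | 0.750 | 125 | 127 |
| 8 v 5 | 0.937 | 0.926 | 102 | 102 |
| 10 v 5 | 0.995 | 0.998 | 74 | 74 |

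The one visible gap is selection of Arm 2 in the 5 v 5 row (0.111 against 0.137). It closes to 0.117 if looks are every 5 patients. Table 1 fits a constant hazard.

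**2. What that model implies.** With median 5 months, 1 - 2^(-2/5) = 24% of events fall before 2 months and 2^(-36/5) = 0.7% of patients are event-free at 3 years.

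**3. What the estimate targets otherwise.** In large samples it is ln 2 × E[min(T, C)]/P(T ≤ C), with T now the EFS time and C the censoring time. Accrual of 200 patients at 5 per month takes 40 months, so C is roughly uniform on 12 to 52 months.

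Assume that a fraction p remits. The others fail between 1 and 2 months (the marrow is due on day 28 ± 7). Remitters have a constant hazard from 1.5 months with an assumed median of 12 months. The true median is 1.5 + 12 × log2(p/0.5). With complete follow-up the exponential figure is ln 2 × (1.5 + 12p/ln 2) = 1.04 + 12p.

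| p | True median | Exponential, complete follow-up | Exponential, planned follow-up | Excess, planned follow-up |
|---|---|---|---|---|
| 0.55 | 3.15 | 7.64 | 7.06 | +124% |
| 0.60 | 4.66 | 8.24 | 7.69 | +65% |
| 0.70 | 7.33 | 9.44 | 8.99 | +23% |
| 0.83 | 10.27 | 11.00 | 10.79 | +5% |

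With complete follow-up the excess at p = 0.70 is 9.44/7.33 - 1 = 29%.

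**4. Keeping the 5-month median and adding the cited 3-year EFS.** For a Weibull curve through S(5) = 0.50 and S(36) = 0.16 or 0.23, the shape is k = ln[log2(1/S(36))]/ln(36/5) = 0.49 or 0.38. The large-sample exponential median is 9.1 or 11.0 months. Through the full design with early stopping, the mean posterior estimate is about 8.1 or 9.5 months, which is 60% or 90% above 5.

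**5. Pairing that trial's EFS with its own CR rates, median left free.** Early failures at 1 to 2 months and then a constant hazard to 16-23% at 3 years give an excess of 14-22% at CR 70% and 2-5% at CR 83%.

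**6. Selection.** With the same non-exponential curve in both arms, total false selection is 0.26-0.30, against 0.27 under the exponential simulation. For 8 v 5 under the two Weibull shapes, selection of the better arm falls from about 0.93 to 0.51-0.55 (k = 0.49) or 0.39-0.40 (k = 0.38). But the hazard ratio is (5/8)^k = 0.79 or 0.84, not 5/8 = 0.625. An approximate log-rank test on all 200 patients (about 154 or 142 events), at one-sided 0.13 to match the design's null selection per arm, has power of 0.62 or 0.48.

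**The case against.** The strongest reply is that a model-free analysis is already planned: Kaplan-Meier, log-rank and Cox stand in the same section. That is right, and a reader should not infer that the posterior is the only EFS analysis. The plan nevertheless assigns the median to the posterior and uses the posterior for the winner rule, so those analyses do not remove the point.

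Second, the size is open to dispute, and this stands. A reader might infer a minimum overstatement of, say, 70%. The documents do not support one:
- The 5-month median, the 50-60% CR and the 16-23% 3-year EFS come from different sources, and the last is from other regimens and another age range. They do not contradict one another as statements about one population.
- The Weibull curves put 14% or 19% of events in the first week, which is hard to square with a day-28 assessment.
- One minus CR overstates resistance, because CRp patients go on to consolidation and non-responders may be re-induced.
- The early-failure argument needs the Section X event definition, and Section VI omits resistance.

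Third, a reader might infer that Table 1 is wrong, or that a better analysis would restore its power. Neither follows. Table 1 is right for a constant hazard, and step 6 shows that most of the lost power comes from the smaller hazard ratio, which a test without the constant-hazard assumption loses as well.

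**Conclusion.** The point holds in limited form. The exponential likelihood is an inference, but a firm one, from the prior and from the reproduction of Table 1. If resistance counts as an event and remission rates are near those cited for fludarabine/ara-C, the reported EFS median and its credible interval would be too high. The excess is about 20-30% at 70% remission, and about 60-100% or more at 50-60% remission or if the 5-month median is combined with the cited 3-year EFS. It is only a few percent at the 83% CR of the anthracycline trial. These figures rest on assumed remission durations, failure times and curve shapes. False selection is barely affected. Table 1's selection probabilities hold only under a constant hazard. The plan should be changed, but the trial's comparison is not invalidated.

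**What to change.** - State the likelihood behind the posterior in Section X.
- Report the Kaplan-Meier median with its confidence interval as the EFS median, and keep the exponential posterior for randomization and monitoring.
- At the final analysis, add Pr(CIA better than FLAI) under a piecewise-exponential model with a break at the end of induction, or a Weibull model, as a sensitivity check.
- Add one non-exponential row to Table 1 and state the hazard ratio it implies.
- Reconcile the EFS event definitions in Sections VI and X.

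The cost is a little more analysis, one more simulation and a less favourable row in Table 1. Sample size, treatment and stopping boundaries do not change.
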